12. STATISTICAL ANALYSIS

- *Describe how your data will be used to test the hypotheses.*
- *State clearly what variables will be tested and what statistical tests will be used.*
- *Include sample size calculations.*
- *If this is a pilot study, state which variables will be examined for hypothesis generation in later studies.*

The sample size of 60 participants was chosen to have a sufficient number of patients to obtain a preliminary assessment of the feasibility of personalized trials of light therapy for management of symptoms of fatigue. The numbers of questionnaires and treatment repetitions per trial were based on expert recommendations by a statistician and estimations about maximal duration of the trial to maintain patient engagement. Specifically, the primary endpoint is trial completion in the first 3 months. We aim to demonstrate a trial completion rate greater than 50% in randomized participants. With $n = 60$, using a one-sample binomial test at 2.5% significance one-sided, this will give us about 90% power if the true completion rate is 70%. Data will be reported transparently so that individual level heterogeneity can be assessed(21).

Participants will be randomized into one of two different treatment orders, ABCCBA or CBAABC, where A=bright light, B=dim light, and C=usual care. Two treatment orders were chosen to test out the feasibility of carrying out a virtual, N-of-1 study. ABCCBA was chosen as an order to test participant acceptability with back-to-back usual care treatment (i.e. no treatment) extending through 4 weeks. CBAABC was chosen as a companion treatment order to ABCCBA to test participant acceptability with starting a Personalized Trial with a usual care treatment after a baseline run-in (i.e. no treatment for the first 4 weeks). Treatment order was not included as a factor in the statistical analysis because acceptability and feasibility study.

The randomization schedule will be set up by a member of the Center for Personalized Health data team and provided to the data analyst assigned to Personalized Trials of Light Therapy for Fatigue. Randomization will occur with a fixed seed value for the purposes of repeatability and auditability, and the list of 60 participants will be split into two groups of 30 using a random shuffle function that takes that seed as input. The order in which an individual becomes eligible for one of these 60 randomizations will determine the placement given (i.e. the first person eligible will be randomized to the treatment order given to participant 1, and continue sequentially). Eligibility is obtained by a participant maintaining at least 80% adherence of survey response, Fitbit wear \geq 12 hours a day, and 80% sleep data available through the baseline run-in period. The data analyst will alert the research coordinator of the assigned randomization once a participant becomes eligible during the baseline run-in period.

The primary outcome measure will be a mean usability score, obtained using the System Usability Scale (SUS), a validated 10-item questionnaire originally developed by John Brooke in 1986 that asks users to score each item on a Likert scale from Strongly Disagree (rating of 1) to Strongly Agree (rating of 5). The SUS will be presented to the participant as addressing the ease of use, complexity, consistency of the Personalized Trials system as a whole, from recruitment to receipt of the report. Individual results are calculated to arrive at a composite measure out of 100. Participant SUS scores will be averaged together. Higher scored values correlate to a more usable system, and therefore a better outcome.

Other outcome measures assessing feasibility of the Personalized Trials framework include:

- Mean participant satisfaction with Personalized Trials components supplemental to the SUS,
- Qualitative satisfaction data collected during the participant phone interview,
- Mean participant survey adherence rate, defined as completion of each assigned survey
- Mean participant Fitbit adherence rate, defined as recorded heart rate data for \geq 12 hours each day,
- Mean participant Fitbit sleep rate, defined as recorded sleep and wake cycles
- Mean participant bright AYO adherence rate, defined as completion of each assigned 30-minute session
- Mean participant dim AYO adherence rate, defined as completion of each assigned 30-minute session
- Google Ad metrics
- Social media activity, including but not limited to:
 - Social media conversion rate, defined as total impressions compared to total click-through
 - Cost per social media conversion
- Website activity, including but not limited to:

- Total number of website visits per traffic source
- Website bounce rates
- Mean user total time on website

In order to share a summary report of observed trends back to the participant to assess acceptability and satisfaction with the participant report, additional outcomes will be analyzed on an N-of-1 level including:

- Mean Within-Subject Difference in Self-Reported Daily Fatigue During 3 Treatment Periods from Mean Baseline using the PROMIS Item Bank v1.0 – Fatigue 7b Daily Short Form
- Mean Within-Subject Difference in Self-Reported Weekly Fatigue During 3 Treatment Periods from Mean Baseline, using the PROMIS Item Bank v1.0 – Fatigue 8a Short Form
- Mean Within-Subject Difference in Ecological Momentary Assessment Three-Times-Daily of Pain During 3 Treatment Periods from Mean Baseline, using the Numeric Pain Rating Scale adapted from McCaffery, Beebe et al. 1989
- Mean Within-Subject Difference in Ecological Momentary Assessment Three-Times-Daily of Fatigue During 3 Treatment Periods from Mean Baseline, using the Numeric Pain Rating Scale adapted from McCaffery, Beebe et al. 1989
- Mean Within-Subject Difference in Ecological Momentary Assessment Three-Times-Daily of Concentration During 3 Treatment Periods from Mean Baseline, using the Numeric Pain Rating Scale adapted from McCaffery, Beebe et al. 1989
- Mean Within-Subject Difference in Ecological Momentary Assessment Three-Times-Daily of Confidence During 3 Treatment Periods from Mean Baseline, using the Numeric Pain Rating Scale adapted from McCaffery, Beebe et al. 1989
- Mean Within-Subject Difference in Ecological Momentary Assessment Three-Times-Daily of Mood During 3 Treatment Periods from Mean Baseline, using the Numeric Pain Rating Scale adapted from McCaffery, Beebe et al. 1989
- Mean Within-Subject Difference in Ecological Momentary Assessment Three-Times-Daily of Stress During 3 Treatment Periods from Mean Baseline, using the Numeric Pain Rating Scale adapted from McCaffery, Beebe et al. 1989
- Mean Within-Subject Difference in Self-Reported Side Effects from Baseline, using the average number of days side effects were reported during treatment periods.
- Mean Within-Subject Difference in Device-Recorded Daily Steps from Mean Baseline, using participant Fitbit data
- Mean Within-Subject Difference in Device-Recorded Nightly Sleep from Mean Baseline, using participant Fitbit data
 - The effects of treatment on sleep quality will be assessed using generalized estimating equations (GEE) with an unstructured

variance-covariance matrix for measures on the same day. This model accounts for possible autocorrelation and linear trends between self-reported sleep quality ratings over time.

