8. NUMBER OF SUBJECTS

- *Indicate the total number of subjects to be accrued locally. If applicable, distinguish between the number of subjects who are expected to be pre-screened, enrolled (consent obtained), randomized and complete the research procedures.*
- *If your study includes different cohorts, include the total number of subjects in each cohort.*
- *If this is multisite study, include total number of subjects across all sites.*

We expect to pre-screen up to 750 potential participants in this study. Up to 150 potential participants will be invited to enroll. Up to 60 participants will be randomized to complete research procedures.

Of those participants who receive randomized treatment schedules, 30 participants will be randomized to receive the protocol in the following order of two-week treatment periods: Bright Blue Light Therapy, Dim Blue Light Therapy, Usual Care, Usual Care, Dim Blue Light Therapy, Bright Blue Light Therapy (ABCCBA). The remaining 30 participants will be randomized in the following order of two-week treatment periods: Usual Care, Dim Blue Light Therapy, Bright Blue Light Therapy, Bright Blue Light Therapy, Dim Blue Light Therapy, Usual Care (CBAABC).

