Baseline participants that do not achieve at least 80% adherence of Fitbit wear and survey submission during the first 10 days of the baseline period will be withdrawn from the study. Those that maintain at least 80% adherence will be randomized to one of two treatment sequences in the pilot study. Participants who are randomized to receive treatment sequences will receive email confirmation including their protocol timeline. Participants will also receive a second mailed kit including a bright blue light commercial AYO light therapy device, and a dim blue light research AYO light therapy device. Enrollment will continue until up to 60 participants have been randomized into one of two treatment sequences.

Each treatment sequence is made up of 6 2-week periods dedicated to either bright blue light therapy, dim blue light therapy, or usual care. During both bright blue light and dim blue light therapy weeks, participants will receive a text message within an hour of their self-reported wake time instructing them to use their designated light therapy device for 30 minutes. During usual care treatment periods, participants will not receive any text notifications to complete light therapy, and will instead be asked to refrain from using either AYO device.

During all treatment weeks (12 weeks total), participants will be asked to continue wearing their Fitbit device each day and night. They will continue to receive 3 randomized text messages each day with questions about their fatigue, pain, concentration, confidence, mood, and stress at that current moment, as well as an

evening text asking them to reflect on their fatigue and any side-effects they may be experiencing from their light therapy treatment (if applicable). Participants will receive slightly longer surveys on Sunday evenings, asking them to reflect on their symptoms of fatigue that week. A study phone number and email address will be available as part of each survey to contact the study team if a participant is concerned about any side effects they are experiencing. Participants will also be instructed to stop their light therapy sessions if they are concerned about their side effects.

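### At n = 60 the exact one-sided 2.5% binomial test has about 84% power at a 70% completion rate; the stated figure of about 90% fits an approximate or mid-p test that the plan does not name

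*Combined protocol and SAP*

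**What the plan says.** Section 12 of the combined protocol and SAP identifies the endpoint: "Specifically, the primary endpoint is trial completion in the first 3 months". It sets the target: "We aim to demonstrate a trial completion rate greater than 50% in randomized participants". For n = 60 the section then states the test and its power: "using a one-sample binomial test at 2.5% significance one-sided, this will give us about 90% power if the true completion rate is 70" per cent.

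Section 12 does not say whether the test is exact, a normal approximation or mid-p. It gives no number of completers at which the 50% rate would be rejected. Section 8 (Number of Subjects) treats 60 as a ceiling: "Up to 60 participants will be randomized to complete research procedures". Section 11 (Research Procedures) does the same: "Enrollment will continue until up to 60 participants have been randomized into one of two treatment sequences".

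**The concern.** The number of completers is a whole number, so a test with a fixed cut-off cannot have a size of exactly 2.5% at n = 60. The available sizes jump from one count to the next, and the power jumps with them. A power figure therefore has a definite meaning only once the version of the test, and hence the cut-off, is known. Section 12 names a binomial test, which most statisticians would take to be exact, but quotes a power that the exact test does not have.

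Two things are at stake, both limited. First, under the exact test the chance of missing a true 70% completion rate is 16%, where the text implies 10%. Second, one possible result (38 of 60) passes under one version and fails under another. With no version named, that choice could be made after the count is known. This is the only power statement in the plan.

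**Working it through.** **Inputs, all from Section 12.** n = 60; null rate p0 = 0.50; alternative rate p1 = 0.70; one-sided level 0.025; analysis in all randomized participants. Failure to complete is itself the adverse outcome, so no allowance for dropout is needed. X is the number of completers.

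**Step 1: reproduce the plan's figure.** Normal approximation without continuity correction:

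power = Φ( [ (p1 − p0)√n − 1.96·√(p0(1 − p0)) ] / √(p1(1 − p1)) )

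- (0.70 − 0.50)·√60 = 1.549
- 1.96 × 0.5 = 0.980
- √(0.7 × 0.3) = 0.458
- (1.549 − 0.980) / 0.458 = 1.242, and Φ(1.242) = 0.893

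This gives 89.3%. The arcsine formula gives 89.0%. The stated figure is therefore reproduced by approximate methods. With a continuity correction, the normal formula gives 86.5%.

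**Step 2: exact size and power by cut-off.** Size is P(X ≥ k | 60, 0.5) and power is P(X ≥ k | 60, 0.7).

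| Cut-off k | Size | Power |
|---|---|---|
| 37 | 4.62% | 93.7% |
| 38 | 2.59% | 89.6% |
| 39 | 1.37% | 83.8% |
| 40 | 0.67% | 76.2% |

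The lowest cut-off with size at or below 2.5% is 39, so the exact test has 83.8% power. The shortfall against the stated figure is 90 − 83.8 = 6.2 points.

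**Step 3: which tests use which cut-off.**

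- Uncorrected score test at 38: z = (38 − 30)/√15 = 2.066, p = 0.0194, so it rejects. At 37: z = 7/√15 = 1.81, below 1.96, so it does not.
- Mid-p at 38: 0.01367 + 0.5 × (0.02595 − 0.01367) = 0.0198, so it rejects. At 37 the mid-p value is 0.0361, so it does not.
- Exact test at 38: p = 0.0259, so it does not reject.
- Continuity-corrected score test at 38: p = 0.0264, so it does not reject. Its cut-off is 39, the same as the exact test.

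A randomized exact test with size exactly 2.5% would have 89.1% power, but it is not a fixed cut-off and the plan does not suggest one.

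**Step 4: how often the choice matters.** At n = 60 the versions differ only when X = 38.

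- At a true rate of 70%: 0.8959 − 0.8382 = 0.0577, or 5.8%.
- At a true rate of 50%: 0.02595 − 0.01367 = 0.0123, or 1.2%.

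**The case against.** The best defence is that 2.5% is a nominal level. Section 12 does not use the word exact and does not promise that the true size stays below 2.5%. A score or mid-p test at nominal 2.5% rejects at 38 of 60 with 89.6% power, so level and power then agree under a single recognised test, and the true size exceeds 2.5% by only 0.09 points. The study is a feasibility pilot, and no decision to proceed is tied to this p-value. Uncertainty elsewhere around this test may also matter more: Section 12 goes on to name a mean usability score as the primary outcome measure.

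Much of this stands. It shows that the power figure is legitimate for some test, and that the practical effect is small. It does not remove the mismatch, because the text names a binomial test with no mention of an approximation or of mid-p, and the ordinary reading gives 84%. The usability score is a separate matter and does not bear on this figure.

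A reader might infer that the sponsor made an arithmetic error. The documents do not support that, since 89.3% is a correct normal approximation. A reader might also infer that the stated level and power cannot be reconciled at all. That follows only if 2.5% is taken as a strict cap on true size with a fixed cut-off, which Section 12 does not say.

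**Conclusion.** The point holds as a mismatch between the named test and the quoted power. The exact one-sided 2.5% test at n = 60 has 83.8% power at a 70% completion rate (cut-off 39, size 1.37%). About 90% needs a cut-off of 38, with a true size of 2.59%. The gap is one completer, or 5.8 points of power between the two cut-offs. It rests on one assumption: that a binomial test without qualification means the exact test. Severity is minor.

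Two further inferences are not supported. One is that the trial needs more participants. Exact power first reaches 90% at n = 65 (cut-off 41, power 91.0%), but Section 12 justifies 60 as enough for a preliminary assessment of feasibility, and about 84% power is reasonable for that purpose. The other is that a recruitment shortfall makes the problem worse. Sections 8 and 11 make 60 a maximum, but no section predicts a smaller number and the power claim is made only for n = 60. A rule for setting the cut-off at a smaller final n is enough.

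**What to change.** Before data are seen, keep n = 60 and replace the power sentence in Section 12 with wording such as:

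> With 60 randomized, the exact one-sided 2.5% binomial test rejects a 50% completion rate if 39 or more complete (actual size 1.4%), giving about 84% power at a true rate of 70%. If fewer than 60 are randomized, the cut-off is the smallest k with P(X ≥ k | n, 0.5) ≤ 0.025.

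If a score or mid-p test was intended, name it instead, state the cut-off of 38 of 60, keep the power at about 90%, and disclose the true size of 2.6%.

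Either version takes about two sentences and adds no participants. The cost of naming the exact test is that the stated power falls from about 90% to about 84%. The cost of the alternative is stating openly that the true size is slightly above 2.5%.

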9. STUDY TIMELINES

- *Describe the duration of an individual's participation in the study*
- *Describe the duration anticipated to enroll all study subjects*
- *The estimated date of study completion*

The study will take place over the course of 14 weeks. The first two weeks will be a baseline period, where no light therapy is assigned, but data are collected, including self-report of fatigue and accelerometer-derived sleep and activity data. After successful completion of the baseline period, participants will be randomized to six 2-week treatment blocks of bright blue light therapy, dim blue light therapy, and usual care. In usual care treatment periods, participants will be instructed to not use any light therapy device and will be asked to continue answering survey questions and wearing their Fitbit device. At the end of the 14 weeks, a report containing the individual's analyzed data will be sent to each participant, along with a satisfaction survey. This report will be sent within 3 months of study completion. After the satisfaction survey is completed, study coordinators will reach out to each participant to interview them about their experience in Personalized Trials. A \$100 pay card (CliniCard) will be mailed to each participant as compensation for their time after the successful completion of 14 weeks of data collection, satisfaction survey, and phone interview.

Potential participants will have the opportunity to choose from within a provided list of start dates during their enrollment process. No more than 20 potential participants will begin their baseline period on the same day. Enrollment will be ongoing until up to 60 participants have been randomized after baseline to receive a personalized trial of light therapy for self-reported fatigue. We estimate that the final participant will be randomized by September 30, 2021, and data collection will cease by December 31, 2021.

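### Treatment order comes from one shuffle of 60, so balance is not assured below 60 randomised or within a start cohort; the exposure is minor and cheap to remove

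*Combined protocol and SAP*

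**What the plan says.** Section 12 describes one fixed-seed shuffle: "the list of 60 participants will be split into two groups of 30 using a random shuffle function that takes that seed as input". List places are then consumed in sequence: "The order in which an individual becomes eligible for one of these 60 randomizations will determine the placement given". No smaller block and no stratification by start date appears anywhere in the document.

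Section 8 plans 30 people on ABCCBA and then says "The remaining 30 participants will be randomized in the following order of two-week treatment periods", meaning CBAABC (A bright light, B dim light, C usual care). The same section makes the total a ceiling: "Up to 60 participants will be randomized to complete research procedures". Section 9 repeats this, "Enrollment will be ongoing until up to 60 participants have been randomized after baseline", and adds a date: "We estimate that the final participant will be randomized by September 30, 2021". No minimum is given.

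Participants start in dated groups. Section 11 has every baseline begin on a Monday, and section 9 sets a cap: "No more than 20 potential participants will begin their baseline period on the same day". That cap applies before the adherence screen in section 11, under which "Baseline participants that do not achieve at least 80% adherence of Fitbit wear and survey submission during the first 10 days" of baseline are withdrawn, so a randomised cohort can be smaller than 20.

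Section 12 gives the acceptability of each sequence as the reason for having two orders (four consecutive weeks of usual care in one, a no-treatment start in the other), and leaves order out of the analysis. Section 4 plans to test pooling of individual results to estimate the overall effect of light therapy. Section 3 names bright light against usual care as a comparison of interest.

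**The concern.** A single shuffle of 60 is one block of 60. It forces equality only at the sixtieth place. If enrolment ends earlier, the planned 30 per order is lost and the split is left to chance. Within a start cohort the split is always left to chance.

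Two uses of the data lean on balance. One is the pooled bright light versus usual care estimate: bright light occupies periods 1 and 6 in one order and 3 and 4 in the other, with usual care the reverse, so some period effects have opposite signs in the two orders and cancel only to the extent that the orders are equally represented. The other is any description of completion, adherence or satisfaction by order, where uneven splits across start dates mix order with calendar time. Because order is not in the analysis, nothing later adjusts for an imbalance.

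**Working it through.** **The plan's own figures.**
- With all 60 places used, the split is 30:30 with probability 1, as section 8 states.
- The power statement in section 12 (n = 60, null 50%, alternative 70%, one-sided 2.5%) reproduces by the normal approximation: Φ((0.20×√60 − 1.96×0.5)/√0.21) = Φ(0.569/0.458) = 89.3%, matching the stated figure of about 90%. Order does not enter this formula. (An exact cut-off that keeps the level at or below 2.5%, 39 of 60, has 83.8% power; that is a separate matter.)

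**Chance of an uneven split.** Among any m consecutive places, the number k on ABCCBA is hypergeometric: P(k) = C(30,k)·C(30,m−k)/C(60,m). The values of m are assumptions, because the documents give neither the size of randomised cohorts nor a stopping point.

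| Assumed situation | Split | Probability |
|---|---|---|
| Cohort of 20 | 12:8 or worse | 41.2% |
| Cohort of 20 | 13:7 or worse | 17.0% |
| Cohort of 20 | 14:6 or worse | 5.4% |
| Cohort of 10 | 7:3 or worse | 29.9% |
| Stop at 40 | 23:17 or worse | 17.0% |
| Stop at 50 | 27:23 or worse | 29.9% |
| Stop at 50 | 28:22 or worse | 8.0% |
| Stop at 55 | 29:26 or worse | 35.3% (30:25 is the worst possible) |

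The expected absolute difference is about 2.9 people at 40 and 2.2 at 50. In 200,000 simulated shuffles with three cohorts of 20, at least one cohort was 13:7 or worse in 35% and 14:6 or worse in 13%; all three were 10:10 in about 5%.

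**What an uneven split does to bright light minus usual care.** Write the period effects shared by participants with the same start date as π1 to π6, and let q = (π1+π6)/2 − (π3+π4)/2.
- A completer on ABCCBA carries +q; a completer on CBAABC carries −q.
- The residue in the mean over n1 and n2 completers is q(n1−n2)/(n1+n2). At 13:7 this is 6/20 = 0.30q; at 23:17 it is 6/40 = 0.15q.
- If the trend is linear, πt = a + bt, then (1+6)/2 = (3+4)/2 = 3.5, so q = 0. The trend cancels within each completer whatever the split. Dim light, at (2+5)/2, also has mean position 3.5.
- Someone who stops after three periods loses this protection: bright minus usual care carries π1−π3 = −2b on ABCCBA and +2b on CBAABC. Linear drift then cancels only through balance between the orders.

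**Efficiency.** For a comparison of the two orders, efficiency relative to an equal split is 4·n1·n2/n². At 23:17 it is 4×23×17/1600 = 98%; at 13:7 it is 4×13×7/400 = 91%.

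**The case against.** The case for leaving the list alone is substantial.

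- No specified test depends on balance. The powered test is a one-sample completion rate in all randomised participants, the usability score is a single mean, and the symptom outcomes are analysed person by person for individual reports. This stands.
- A reader might infer that shared period effects cancel only when both orders are equally represented on the same dates, so that gradual daylight change would bias the results. The design does not support that: steady drift cancels within each completer. With all 60 randomised and completing, cohort imbalances also sum to zero, so curvature common to every cohort cancels in the pooled contrast.
- This is chance imbalance, not systematic bias. Allocation is random, so order is unrelated to start date in expectation. This stands, and the loss of efficiency is small.
- Members of a start cohort do not share conditions exactly. Section 11 allows pauses, and section 6 recruits across the whole country, so daylight differs within a cohort. This limits what balancing by date could achieve.
- A reader might infer that enrolment will fall short. The documents only allow it: section 9 continues enrolment towards 60, section 8 allows up to 150 invitations, and the September date is an estimate, not a stopping rule.

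The narrower exposure remains. Order-specific acceptability is the stated reason for two orders, pooling is a stated aim, order is not adjusted for, and a plan that tests completion against 50% and is powered at 70% must expect incomplete sequences.

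**Conclusion.** The concern holds as a minor weakness of the allocation method. The stated 30:30 depends on filling all 60 places, and balance within a start cohort is left to chance. Under the assumed sizes, a 13:7 cohort or a 23:17 total at a stop of 40 each has probability 17% (that split or worse). At those splits 0.30 or 0.15 of the non-linear period effect q stays in the bright light versus usual care contrast. The documents give no value for q, so the effect in fatigue units is unknown.

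The exposure is confined to non-linear or cohort-specific calendar effects and incomplete sequences in the pooled estimate, and to descriptive reading of acceptability by order. It would be wrong to conclude that the primary completion result, the mean usability score or any participant's own report is compromised: none of them compares orders across participants.

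**What to change.** In section 12, replace the single shuffle with a seeded list of permuted blocks of mixed size 2 and 4, totalling 60 and used in order of eligibility as now.

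- At 60 the split is still exactly 30:30.
- The running difference returns to 0 at each block end and never exceeds 2, so the overall difference is at most 2 wherever enrolment stops. A stop at 40 is then no worse than 21:19, a residue of at most 2/40 = 0.05q.
- Any run of consecutive places, such as a start cohort, differs by at most 2 + 2 = 4. A cohort of 20 is then no worse than 12:8, a residue of at most 4/20 = 0.20q.

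The cost is a few lines in the randomisation script; the fixed seed and audit trail are kept. The downside is slightly more predictability near the end of a block. Mixed block sizes limit it, as does withholding the list from the coordinator, who would still be told each assignment only once that person is eligible.

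Permuting separately within each start cohort, with the odd person assigned at random, would balance dates more tightly but can lose the exact 30:30. With four odd-sized cohorts it is missed with probability 1 − 6/16 = 62.5%; with six, 1 − 20/64 = 69%. If that route is chosen, the protocol should say so.
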